12.3 Untoward Medical Occurrences

Untoward medical occurrences occurring before the first exposure to IP are not considered AEs (according to the definition of AE, see Section 12.1.1). However, each **serious** untoward medical occurrence experienced before the first IP exposure (ie, from the time of signed informed consent up to but not including the first IP exposure) will be described on the AE CRF and SAE Report Form. These events will not be considered as SAEs and will not be included in the analysis of SAEs.

For the purposes of this study, also each non-serious untoward medical occurrence experienced by a subject undergoing endoscopy or other procedure to obtain a biopsy for the diagnosis of GvHD before the first IP exposure will be recorded on the AE CRF; these events will not be considered as AEs and will not be included in the analysis of AEs.

12.4 Non-Medical Complaints

A non-medical complaint (NMC) is any alleged product deficiency that relates to identity, quality, durability, reliability, safety and performance of the product but **did not result in an AE**. NMCs include but are not limited to the following:

- A failure of a product to exhibit its expected pharmacological activity and/or design function, eg reconstitution difficulty
- Missing components
- Damage to the product or unit carton
- A mislabeled product (eg, potential counterfeiting/tampering)
- A bacteriological, chemical, or physical change or deterioration of the product causing it to malfunction or to present a hazard or fail to meet label claims

Any NMCs of the product will be documented on an NMC form and reported to the sponsor within 1 business day. If requested, defective product(s) will be returned to the sponsor for inspection and analysis according to procedures.

12.5 Medical, Medication and Non-Drug Therapy History

At screening, the subject's medical history will be described for the following body systems including severity (defined in Section 12.1.2.1) or surgery and start and end dates, if known: eyes, ears, nose and throat; respiratory; cardiovascular; GI; musculoskeletal; neurological; endocrine; hematopoietic/lymphatic; dermatological; and genitourinary.

All medications taken and non-drug therapies received from providing informed consent until completion/termination will be recorded on the concomitant medications and non-drug therapies CRFs.

12.6 Physical Examinations

At screening and subsequent study visits (as described in [Table 1](#)), a physical examination will be performed including the following body systems: general appearance, head and neck, eyes and ears, nose and throat, chest, lungs, heart, abdomen, extremities and joints, lymph nodes, skin and neurological. At screening, if an abnormal condition is detected, the condition will be described on the medical history CRF. At study visits, if a new abnormal or worsened abnormal pre-existing condition is detected, the condition will be described on the AE CRF. If the abnormal value was not deemed an AE because it was due to an error, due to a preexisting disease (described in [Section 12.1.1.5](#)), not clinically significant, a symptom of a new/worsened condition already recorded as an AE, or due to another issue that will be specified, the investigator will record the justification on the source record.

12.7 Clinical Laboratory Parameters

12.7.1 Hematology and Clinical Chemistry

The hematology panel will consist of complete blood count (hemoglobin, hematocrit, erythrocytes [ie, red blood cell count] and leukocytes [ie, white blood cell count]) with differential (ie, basophils, eosinophils, lymphocytes, monocytes, neutrophils), mean corpuscular volume, mean corpuscular hemoglobin concentration and platelet counts.

The clinical chemistry panel will consist of sodium, potassium, chloride, bicarbonate, total protein, albumin, alanine aminotransferase, aspartate aminotransferase, total bilirubin, alkaline phosphatase, blood urea nitrogen, creatinine and glucose.

The coagulation panel will consist of prothrombin time (PT), partial thromboplastin time (PTT) and international normalized ratio (INR).

Blood will be obtained for assessment of hematology, clinical chemistry and coagulation panel parameters at screening and other study visits indicated in [Table 2](#). Clinical laboratory assessments should also be performed whenever clinically indicated.

Hematology and clinical chemistry assessments will be performed on ethylenediaminetetraacetic acid (EDTA)–anticoagulated whole blood and serum, respectively, at the local laboratory. The coagulation panel assessment will also be performed at the local laboratory.

12.7.2 Urinalysis

The urinalysis assessments will consist of color, specific gravity, pH, protein, glucose, ketones, bilirubin, urobilinogen, blood, nitrate, leukocyte esterase and microscopic examination (red and white blood cells, bacteria and casts). Urine samples will be obtained at screening and other study visits indicated in [Table 2](#). Urinalysis will be performed at the local laboratory.

12.7.3 Assessment of Laboratory Values

12.7.3.1 Toxicity Grading Scale

Laboratory values will be evaluated according to the NCI CTCAE version 4.03 toxicity grading scale by the investigator.

12.7.3.2 Assessment of Abnormal Laboratory Values

For each abnormal laboratory value, the investigator will determine whether the value is considered clinically significant or not. For clinically significant values, the investigator will indicate if the value constitutes a new AE (see definition in [Section 12.1](#)) or if the value is related to a previously recorded AE. Any clinically significant abnormal laboratory finding associated with a pre-existing condition (described in [Section 12.1.1.5](#)) or GvHD will not constitute an AE, unless judged by the investigator to be more severe than expected for the subject's condition. The investigator will also record the severity grading (only if 3 or 4) within the respective laboratory page of the eCRF for a clinically significant laboratory value that constitutes an AE, and the severity grades for the sign, symptom or medical diagnosis in the AE page of the eCRF. Regarding clinically significant abnormal laboratory values that are adverse events, only the highest severity grading will be reported in the eCRF. Regardless of the severity grade, an AE will be followed until resolution or until no longer deemed necessary by the investigator.

If the abnormal value was not clinically significant, the investigator will indicate the reason, ie due to periodic variation, due to a lab error, or due to another issue that will be specified. Additional tests and other evaluations required to establish the significance or etiology of an abnormal value, or to monitor the course of an AE should be obtained when clinically indicated. Any abnormal value that persists should be followed at the discretion of the investigator.

Regarding laboratory abnormal values that are adverse events, only the highest grading will be reported in the eCRF. Regardless of the grade, the AE will be followed until resolution or until no longer deemed necessary by the investigator.

12.7.4 Backup Samples and Biobanking

Backup samples taken and stored short-term may be used for example for re-testing, follow-up of an AE(s) or other test results and/or assay development for this study only. After study testing is completed, the remaining samples may be stored in a coded form for no more than 2 years after the final study report has been completed and then the samples will be destroyed.

Backup samples from a subject who has withdrawn consent will not be used for additional testing after the subject withdraws consent.

For this study, no samples will be taken or stored long-term in biobank(s) for future analyses.

12.8 Vital Signs

Vital signs will include body temperature (°C or °F), respiratory rate (breaths/min), pulse rate (beats/min) and systolic and diastolic blood pressure (mmHg). Height (in or cm) and weight (lb or kg) will also be collected.

Vital signs will be measured at screening and within 30 minutes before and after administration of IP at the study visits indicated in [Table 1](#). Height will be collected only at the screening visit. Blood pressure will be measured when subjects are in the sitting position; measurements in the supine position will also be acceptable if the subject is too ill to sit.

Vital sign values are to be recorded on the CRF. For each abnormal vital sign value, the investigator will determine whether or not to report an AE (see definition in [Section 12.1](#)) and record the medical diagnosis (preferably), symptom or sign on the AE CRF.

Additional tests and other evaluations required to establish the significance or etiology of an abnormal value, or to monitor the course of an AE should be obtained when clinically indicated. Any abnormal value that persists should be followed at the discretion of the investigator.

12.9 Electrocardiogram

An ECG will be performed at screening to assess eligibility. Subjects should be in a supine or semi-supine position for at least 5 minutes prior to the assessment.

All ECG printouts must be reviewed by the investigator or a medically qualified member of the site staff and annotated to indicate any clinical finding. Prior to the first dose of study treatment, any ECG abnormality must be documented by the investigator as not medically relevant

The ECG assessments (normal vs abnormal) are to be recorded on the CRF. For each assessment, the investigator will determine whether the assessment is considered an AE (see definition in Section 12.1 and record the sign, symptom, or medical diagnosis on the AE CRF). Additional tests and other evaluations required to establish the significance or etiology of an abnormal assessment, or to monitor the course of an AE should be obtained when clinically indicated. Any abnormal assessment that persists should be followed at the discretion of the investigator.

12.10 Pregnancy Test

A serum pregnancy test will be performed for females of childbearing potential only at screening and Day 56.

12.11 Recurrent Malignancy

At screening and all visits during the study, subjects will be assessed for recurrent malignancy. Recurrent malignancy must be confirmed by a biopsy, per standard institutional practice. The investigator will record the presence or absence of recurrent malignancy in the eCRF.

13. STATISTICS

13.1 Sample Size and Power Calculations

Part 1:

The sample size for Part 1 was determined from an operational perspective and was not based on statistical power considerations. With 20 evaluable subjects and an assumed true response rate of 65%, the probability of observing an overall response rate of at least 55% is 87.8%. If the true response rate is 40%, the probability of observing an overall response rate of 55% or higher is less than 13%.

Part 2:

The primary endpoint for Part 2 is the overall response rate at Day 28.

The null hypothesis for Part 2 is that there is no difference in the overall response rate at Day 28 between the 2 treatment groups. The alternative hypothesis is that the overall response rate at Day 28 of the GLASSIA group is higher than that of the control group.

To determine the sample size for Part 2, the following assumptions were used:

1. Control group overall response rate of 40% across strata
2. GLASSIA group overall response rate of 65% across strata
3. Randomization ratio 1:1
4. 1-sided family wise Type I error rate of 0.025
5. Type II error rate of 0.20 (ie, power=80%)
6. A group sequential design with 1 interim look will be applied to the study. The gamma error spending function³¹ with a parameter -2 will be used for beta spending (nonbinding). The interim analysis will take place when approximately 50% of the primary endpoint data has been accumulated

SAS version 9.4, PROC SEQDESIGN with stop=both and nonbinding option for beta, and a gamma parameter of -40 for alpha spending (and hence no alpha spent) and -2 for beta spending was used to calculate this design.

Based on the sample size calculations, using a Cochran-Mantel-Haenszel chi-squared test, controlling the stratification factor, to detect the difference between the 2 groups, the primary analysis will require 67 evaluable subjects per group. Assuming a 10% early withdrawal rate, the target number of subjects will include 74 randomized subjects per group for a total of 148 randomized subjects.

The early withdrawal rate will be monitored in a blinded manner, and if found to be greater or less than 10%, sample size assumptions may be revised.

13.2 Analysis Sets

Part 1

The **Efficacy Analysis set** will include all subjects who are evaluable for overall response at Day 28. Subjects who receive at least 1 dose of study treatment and who have a lower GI biopsy that is consistent with acute GvHD will be considered evaluable.

The **Per-Protocol Analysis set** will include all subjects who received at least 1 dose of study treatment, meet all key eligibility criteria, and have no major or clinically significant protocol deviations. Major protocol deviations that will lead to exclusion from this set will be determined prior to each database lock.

The **Safety Analysis (SAF) set** will consist of all subjects who receive at least 1 dose of study treatment.

The **PK Analysis set** will consist of all subjects in the SAF set who have at least 1 PK or stool sample collected.

Part 2

The **Full Analysis (FA) set** will include all subjects who are randomized at Day 0. Following the intent-to-treat principle, subjects will be analyzed according to the treatment they are assigned to at randomization.

The **Per-Protocol Analysis set** will include all subjects who received at least 1 dose of study treatment, meet all key eligibility criteria, and have no major or clinically significant protocol deviations with a lower GI biopsy consistent with acute GvHD and without a major protocol deviation. Major protocol deviations that will lead to exclusion from this set will be prespecified prior to unblinding the treatment codes.

The **SAF set** will consist of all subjects who receive at least 1 dose of study treatment. Subjects will be analyzed according to the treatment received.

The **PK Analysis set** will consist of all subjects in the SAF set who have at least 1 PK or stool sample collected.

13.3 Handling of Missing, Unused, and Spurious Data

Part 1

For the analysis of the primary and key secondary efficacy endpoints, subjects who do not have a response assessment at Day 28 will be classified as non-responders. This approach will also be applied to the analysis of other time point responses, including the overall response at Day 56. A sensitivity analysis will be performed for the primary and key secondary efficacy endpoints using the last-observation-carried-forward (LOCF) approach to impute the missing response assessment.

Part 2

For the primary analysis of the primary endpoint, subjects who do not have an overall response evaluation at Day 28 will be classified as non-responders. If there are more than 5% subjects missing for the primary endpoint in either treatment group, 2 sensitivity analyses will be carried out. In the first analysis, missing data will be imputed with a missing-at-random assumption. This approach will assume that subjects who withdraw from a treatment group had missing values similar to subjects in that treatment group who completed the study. The second analysis will be a control-based imputation for the GLASSIA group (“jump to reference”). This approach will assume that subjects who withdraw had missing values similar to subjects in the control group who completed the study, regardless of the assigned treatment.

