8.2.2 Part 2 Study Design

Criteria for Initiation of Part 2

The following decision criteria will be followed for the initiation of Part 2 of the study:

- The study may be terminated by the sponsor for toxicities or adverse safety findings observed in Part 1 of the study
- The study may proceed to Part 2 if an overall response rate of $\geq 55\%$ is observed at Day 28 in Part 1, as determined by the sponsor

- The study may be stopped for futility if the overall response rate is <55% at Day 28
- The sponsor will be the final arbiter of the decision to move into Part 2. The decision will be based on the totality of cumulative data available (eg, rate of GvHD CR, PR and very good partial response [VGPR]; rate of GI CR and PR, including response at Days 28 and 56; duration of any overall and any GI response; and GvHD-free survival)

Study Design for Part 2

Part 2 of this study is a randomized, parallel-group, double-blind, placebo (albumin)-controlled, clinical study comparing GLASSIA in combination with conventional steroid treatment versus albumin (control) in combination with conventional steroid treatment. Part 2 of the study is planned to enroll approximately 148 randomized subjects (74 subjects/group) in order to obtain 134 evaluable subjects, provided that the study does not stop early for futility.

On Day 0, eligible subjects will be randomized 1:1 in a double-blind fashion to the following groups:

Group 2a: GLASSIA with a loading dose of 90 mg/kg (Day 0) followed by GLASSIA 30 mg/kg every other day (Days 2 to 12), then followed by 120 mg/kg weekly (Days 14 to 49), in combination with 2 mg/kg/day methylprednisolone or equivalent steroid

Group 2b: Albumin (control) in combination with 2 mg/kg/day methylprednisolone or equivalent steroid

Randomization will be stratified, using a single stratification factor: lower GI involvement severity (2 strata), as described in Section 8.5.1. Subjects who are randomized to treatment in Part 2 and subsequently discontinue treatment or withdraw from the study will not be replaced.

Interim Analyses

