8.4.2 Secondary Outcome Measures

8.4.2.1 Efficacy (Parts 1 and 2)

Key Secondary Efficacy Outcome Measures

1. Proportion of subjects achieving GI response at Day 28. Gastrointestinal response is defined as GI CR + PR, which are defined as follows:
 - GI CR is defined as
 - a) Able to eat; not requiring parenteral nutrition, and
 - b) Passing primarily formed stools
 - GI PR is defined as
 - a) Decrease in need for parenteral nutrition to $\leq 50\%$ of required calories; and
 - b) Reduction of stool volume by $\geq 50\%$, without ileus

Other Secondary Efficacy Outcome Measures

1. Proportion of subjects achieving overall response at Day 56
2. Change from baseline in acute GvHD grading at Days 28, 56 and 180
3. Incidence of chronic GvHD at Days 100, 180 and 365

4. Duration of any overall response
5. Duration of any GI response
6. Overall survival through Days 100, 180 and 365
7. Transplant-related mortality at Days 28, 56, 100 and 180
8. Failure-free survival at Days 100 and 180
9. GvHD-free survival at Days 28, 56, 100 and 180
10. Infection-related mortality at Days 28, 56, 100 and 180
11. GvHD-related mortality at Days 28, 56, 100 and 180
12. All-cause mortality at Days 28, 56, 100 and 180

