13.5 Planned Interim Analysis of the Study

Part 1

An analysis will be performed to determine whether continuation from Part 1 to Part 2 is warranted. It will be performed when the last subject in Part 1 has completed the GvHD response assessment at Day 28. The overall response rate at Day 28 will be analyzed, as well as the data collected at baseline, efficacy as measured by secondary efficacy outcome measures, and safety data.

The analysis will be assessed by the Sponsor. The study may proceed to Part 2 if an overall response rate of $\geq 55\%$ is observed at Day 28 in Part 1. The criteria for initiation of Part 2 are specified in Section 8.2.2.

Part 2

A group sequential design with 1 interim look (Part 2) will be applied to the study. The gamma error spending function³¹ with a parameter -2 will be used for beta spending (nonbinding). SAS version 9.4, PROC SEQDESIGN with stop=both and nonbinding option for beta, and a gamma parameter of -40 for alpha spending (and hence no alpha spent) and -2 for beta spending was used to calculate this design.

The interim analysis will take place when approximately 50% of the primary endpoint data for Part 2 has been accumulated (ie, approximately 67 evaluable subjects with Day 28 assessments).

An independent, unblinded biostatistics team will perform the interim analysis and present the results to the DMC. The study will be analyzed for futility based on the overall response at Day 28 in Part 2. The DMC will provide recommendations to the sponsor based on the interim analysis. However, the sponsor may decide to stop the trial even if statistical criteria for futility are not observed.

With the aforementioned spending functions, the DMC will recommend the study be stopped for futility if the nominal p-value is larger than 0.3430. The type II error spend at the interim analysis is 0.0538. As the interim analysis may not occur when exactly 50% of the primary endpoint data are accrued, the boundary may be adjusted at the analysis time using the specified gamma function (ie, a parameter of -2). A total of 134 evaluable subjects (67 per group) is planned.

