5.1 Handling of Missing, Unused, and Spurious Data

For Part 1, for the primary analysis of GvHD overall response, the non-responder imputation (NRI) approach will be used to impute the response status at Day 28 as no response for subjects without a response assessment at Day 28 due to any reason. The NRI approach will also be applied to GI response at Day 28 and other time point responses, including overall response at Day 56.

Regarding missing data in AE records:

- Handling of unknown causality assessment:
 - If a subject experiences an AE with a missing causality assessment, the relationship of the AE will be counted as “related”.
- Handling of unknown severity grades:
 - If a subject experiences more than one AE categorized under the same preferred term, the subject will be counted under the most severe toxicity grade reported for that AE.
 - If a subject experiences an AE and the toxicity grade was not provided, the toxicity grade of this AE should be counted as “unknown”. A row or column labelled “Unknown” should be inserted for those AEs in tables where AEs are summarized by toxicity grade.

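### At the Part 1 go/no-go look, non-responder imputation at Day 56 does not exempt visits not yet due, so the supportive Day 56 response rates are biased downward

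*Protocol*

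**What the plan says.** On the timing of the Part 1 decision analysis, Protocol 13.5 states: "It will be performed when the last subject in Part 1 has completed the GvHD response assessment at Day 28". Besides Day 28 overall response and baseline data, that analysis covers "efficacy as measured by secondary efficacy outcome measures, and safety data". The first of the other secondary efficacy measures in Protocol 8.4.2.1 is "Proportion of subjects achieving overall response at Day 56".

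Protocol 8.2.2 sets the numerical criterion, an overall response rate of at least 55%, at Day 28. It then leaves the final decision to the sponsor on all the data to hand. Its list of examples includes "rate of GI CR and PR, including response at Days 28 and 56", along with duration of response and GvHD-free survival.

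Protocol 13.3 (Part 1) treats a subject with no Day 28 response assessment as a non-responder and continues: "This approach will also be applied to the analysis of other time point responses, including the overall response at Day 56". The last-observation-carried-forward sensitivity analysis in that section covers only the primary and key secondary endpoints, both at Day 28.

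SAP 5.1 imputes "no response for subjects without a response assessment at Day 28 due to any reason" and in its next sentence extends the method to other time points, Day 56 included. SAP 7.2.2 applies it to overall response at Day 56, and SAP 11.1 to GI CR and PR at Days 28, 56 and 180. SAP 5 takes percentages out of the whole analysis set unless stated otherwise. Protocol 13.2 defines evaluability by dosing and biopsy, so a subject not yet at Day 56 stays in the denominator.

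**The concern.** The rule does not distinguish an assessment that was missed from one that is not yet due. For a missed visit, scoring non-response is a defensible conservative choice. For a visit still in the future it is an artefact of the calendar.

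At the trigger the last subject is 28 days into the study, so that Day 56 visit cannot have taken place. The same holds for anyone enrolled in the preceding 28 days. If all of them score as non-responders, the Day 56 overall and GI response rates before the sponsor are too low, and the shortfall reflects recent accrual rather than the drug.

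The comparison most exposed is Day 28 against Day 56. Every subject has reached or left Day 28, so only the later rate is depressed, and a response that is holding could appear to fade. Protocol 6.1.1 justifies dosing to Day 49 by the wish to sustain response, so that comparison is likely to be looked at.

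**Working it through.** **1. The plan's own figures.** Protocol 13.1 gives 20 evaluable subjects and a 55% threshold, which is 11 of 20. The exact binomial tails are:

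- P(X ≥ 11 | n = 20, p = 0.65) = 0.8782. The protocol states 87.8%.
- P(X ≥ 11 | n = 20, p = 0.40) = 0.1275. The protocol states less than 13%.

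Both reproduce. They concern Day 28, which no subject still has ahead at the trigger, so the imputation at Day 56 does not alter them.

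**2. How many subjects are pending.** No Part 1 accrual rate is given; Protocol 8.3 gives only about 2 years of recruitment for the whole study. Assume 20 subjects at even intervals. The spacing is g = months × 30.4375 / 19 days. The subject enrolled k places before the last has been on study 28 + k × g days at the trigger, and is pending if this is below 56. Let m be the number pending. Using 55 days, to allow for the 1-day visit window, gives the same m in every row below.

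**3. What the rule prints.** With all m pending subjects scored as non-responders and kept in the denominator, the expected Day 56 rate is p × (20 − m)/20, and the bias is −p × m/20. Take p = 65% as an illustration; the documents assume that value for Day 28, not Day 56.

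| Part 1 accrual | Spacing (days) | m | Expected printed rate | Bias (points) |
|---|---|---|---|---|
| 24 months | 38.4 | 1 | 0.65 × 19/20 = 61.75% | −3.25 |
| 18 months | 28.8 | 1 | 61.75% | −3.25 |
| 12 months | 19.2 | 2 | 0.65 × 18/20 = 58.5% | −6.5 |
| 6 months | 9.6 | 3 | 0.65 × 17/20 = 55.25% | −9.75 |
| 4 months | 6.4 | 5 | 0.65 × 15/20 = 48.75% | −16.25 |

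**4. What a denominator set by enrolment date prints.** Among the 20 − m subjects enrolled early enough, the expected rate is p for any m, provided response does not depend on when a subject enrolled.

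**5. Why early failures among recent enrollees should not be added back.** Take m = 3, so 17 subjects are mature with 0.65 × 17 = 11.05 expected responders. Suppose one of the three recent enrollees has already failed. Adding only that subject gives 11.05/18 = 61.4%. Recent failures enter while recent responders are left out, so the selection depends on outcome and a downward bias remains.

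**The case against.** The strongest reply is that this does not touch the decision rule. The only numerical criterion is Day 28 overall response. Day 56 enters as one example in a list, with no threshold, and Part 1 has no formal testing. That is correct. A reader might infer that the go/no-go criterion or its 87.8% is biased; the documents do not support that.

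Second, durability is measured better elsewhere. Duration of response and GvHD-free survival are on the same list in Protocol 8.2.2, and SAP 7.2.2 estimates them by Kaplan-Meier with censoring at the last assessment. Subjects short of Day 56 are handled correctly there. Part 1 is also open-label with responses listed by visit, so pending subjects would be visible. This limits the harm but does not correct the printed Day 56 rates.

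Third, a visit not yet due need not be called missing. The secondary measures run to Day 365 and cannot all be complete at the trigger, so Protocol 13.5 may simply mean data to date. A programmer might well read it that way. The text does not say so, however, and the rule as written gives the other result. By contrast, Protocol 13.4 holds the Part 2 primary analysis until all subjects complete Day 56 or discontinue treatment.

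Fourth, the SAP carries less weight than it seems to. It follows the original protocol, whereas the Part 1 interim text came with Amendment 1, and its any-reason wording sits in a sentence about Day 28. This stands: the point rests mainly on Protocol 13.3 read with 13.5 and 8.2.2.

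Finally, a reader might infer that at least one subject in 20 is always misclassified. That goes too far. At least one visit is always not yet due, but a last subject who has failed, died or would not be in response at Day 56 is scored correctly.

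**Conclusion.** The concern holds in a limited form. Followed as written, the imputation rule makes the Day 56 response rates at the Part 1 decision too low by p × m/20. At a true rate of 65% that is about 3 points with 1 subject pending, 6.5 with 2, 10 with 3 and 16 with 5. These sizes rest on an assumed evenly spaced enrolment and an illustrative true rate; bunched enrolment near the end would enlarge them. The direction does not depend on those assumptions.

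The bias is confined to supportive data at one descriptive look and disappears once all Part 1 subjects have passed Day 56. It had no effect on results: SAP 1 records that the study was terminated after one subject was enrolled and that the planned analyses no longer apply. Severity is minor to moderate. A must-fix rating would need an effect on the Day 28 criterion or on the main durability measures, and the documents show neither.

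**What to change.** Add one sentence to Protocol 13.3 or 13.5, and to SAP 5.1: at the Part 1 decision, response rates at Day 56 and later are reported only for subjects enrolled at least 57 days before the data cut (Day 56 plus the 1-day window), or the matching interval for later visits (for Day 180, 180 + 5 = 185 days), whatever their outcome so far. Within that group, non-responder imputation applies as now, so subjects who died, failed or left still count as non-responders. Show the denominator and the number not yet due beside each rate. Do not add early failures or deaths among more recent enrollees to that denominator.

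The cost is a slightly smaller Day 56 denominator at this look: 17 to 19 of 20 for accrual over 6 to 24 months, under the even-spacing assumption. Nothing changes at Day 28 or in the final Part 1 Day 56 summary.
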